8.8 Study Exposure

The number and percentage of subjects will be provided by number of infusions. For each cohort, the total number of infusions, total cumulative dose (mg), duration of exposure (months), and relative dose intensity will be summarized. The total cumulative dose is calculated as the sum of

actual dose within each study cycle. The duration of exposure is calculated as the time between the date of first dose to the date of last dose plus 14 or 21 days depending on NKTR dosing frequency or end of treatment date, whichever is earlier. The relative dose intensity is calculated as the actual dose intensity divided by the planned dose intensity. The actual dose intensity is calculated as the total cumulative dose divided by weight at baseline and duration of treatment.

Treatment exposure will be summarized for the safety and PK population.

All treatment exposure data will be listed by subject.

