
Key Inclusion Criteria:
	
For each dose escalation cohort, the first subject enrolled to the cohort will be treated on Cycle 1 Day 1 and monitored for tolerance through Cycle 1 Day 5 prior to dosing of the additional subjects at that dose level. Safety data from Cycle 1 will be utilized to assess dose escalation for each new cohort.
 
A DLT is defined as a Grade 3 or higher study-drug-related or possibly related adverse event (AE) occurring within the first cycle of dosing (excluding Grade 3/4 transient lymphopenia < 14 days in duration, tumor flare defined as local pain, irritation, or rash localized at sites of known or suspected tumor, a transient, reversible ≤ grade 3 infusion AE (< 24 hours), non-clinically significant laboratory abnormalities, or fatigue lasting less than 72 hours) using National Cancer Institute (NCI) Common Terminology Criteria for AEs (CTCAE) version 4.03.
 
Part 2: Dose Expansion
 
Enrollment into the renal cell carcinoma cohort may commence once the MTD or RP2D has been determined.
 
Subjects in the dose expansion cohort will be treated every 21 days (q21d), every 14 days (q14d), or every 28 days (q28d) until tumor progression (treatment may continue if there is clinical benefit as determined by the Investigator), death, unacceptable toxicity, symptomatic deterioration, achievement of maximal response, subject’s choice, the Investigator’s decision to discontinue treatment, the subject withdraws consent or Nektar Therapeutics decides to terminate the trial.
 
For Parts 1 and 2:
 
 
• Willing and able to provide written informed consent.
 
• Histologically confirmed diagnosis of a locally advanced (not amenable to curative therapy such as surgical resection) or metastatic solid tumor.
 
• Male or female patients, age 18 years or older at the time of signing the informed consent form (ICF).
 
• Life expectancy > 12 weeks.
 
• Patients must not have received interleukin-2 [IL-2] therapy within 12 months of Cycle 1 Day 1.
 
• Eastern Cooperative Oncology Group (ECOG) performance status 0 to 1.
 
• Measurable disease per RECIST version 1.1.
 
 
For Part 2 only:
 
Renal Cell Carcinoma (RCC)
 
 
a. Histologically confirmed diagnosis of unresectable or metastatic RCC with predominantly clear cell elements.
 
b. Must have received only 1 prior line of anti-angiogenic therapy
 
c. Must not have received prior immunotherapy with immune-modulators including but not limited to checkpoint inhibitors such as anti-PD-1, anti-PD-L1, anti-CTLA-4 antibody and any other antibody or drug specifically targeting T cell co-stimulation or checkpoint pathways, indoleamine 2,3-dioxygenase pathway inhibitors, cancer vaccines, adoptive cell therapies, and cytokine therapies.
 
	

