**Table 4: Part 1: Sample Dose Escalation Scheme**

Cohort	NKTR -214 Dose
Cohort 1	0.003 mg/kg
Cohort 2	0.006 mg/kg
Cohort 3	0.012 mg/kg
██████	██████
██████	██████
██████	██████

The Sponsor and at least one Investigator will jointly decide the following:

- Dose levels for a given cohort, as listed in **Table 4**, may be reduced by 25-50% depending on the severity, duration, and frequency of toxicities observed at the previous dose level as well as the PK profile, if available.
- In the event that MTD is not determined at the highest dose level listed in the table, dose escalation at no more than 100% higher than previous dose may continue.
- The schedule of dosing can be modified to every 14 or 28 days based on a review of the safety data and available PK data.
  - Note, the first dose level for every 14-day cohort will be determined as follows:  
If MTD has been reached in the 21-day dosing cohort, the dosing level will be at least one dose lower than MTD. If MTD has not been reached in the 21-day dosing cohort, the dosing level will be at least one dose lower than the highest dosing cohort tested in the 21-day dosing cohort.
  - The first dose level for every 28-day cohort will be either the MTD using the 21-day dosing cohort (if determined) or the highest dosing cohort tested in the 21-day dosing cohort (if MTD not determined).
- Once the MAD has been reached, lower doses and different dose schedules may be assessed, within the anticipated total number of subjects of approximately 50.

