### **6.11 Administration of NKTR-214**

The subject's weight in kilograms will be determined before the start of each cycle. Each subject's NKTR-214 dose will be determined by the dose escalation scheme and the subject's weight in kilograms. NKTR-214 will be administered as an intravenous (IV) infusion over  $15 \pm 5$  minutes.

Pre-medications should not be administered prior to the initial administration of NKTR-214, but if a subject reports symptoms (such as nausea and/or vomiting), prophylactic use of anti-emetics may be used.

The administration of NKTR-214 will be captured in the source documents and recorded on the electronic case report form (eCRF). The lot number for the NKTR-214 vials will be captured on Drug Accountability Log.

Refer to the Pharmacy Binder for further information.

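### SAP 8.8 gives no 28-day interval in its exposure formula and divides by baseline weight, so exposure figures are off for q28d subjects and for subjects whose weight changes

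*SAP*

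**What the plan says.** SAP 8.8 defines duration of exposure as the time from first to last dose "plus 14 or 21 days depending on NKTR dosing frequency", limited by "or end of treatment date, whichever is earlier". It gives no value for a 28-day interval. On intensity it states: "The actual dose intensity is calculated as the total cumulative dose divided by weight at baseline and duration of treatment". It then adds: "The relative dose intensity is calculated as the actual dose intensity divided by the planned dose intensity". Planned dose intensity is not defined. The second formula also speaks of duration of treatment, whereas the term defined is duration of exposure.

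The protocol allows a third interval:

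- Part 1, under Table 4: "The schedule of dosing can be modified to every 14 or 28 days", on review of safety and PK data, with a rule for where a 28-day cohort starts.
- Part 2: the synopsis lists 14-, 21- and 28-day dosing.
- Section 6.3 repeats the option, and the visit schedules (Tables 1 and 2) carry a Day 22 column used only for 28-day cycles.

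SAP section 3 itself foresees other schedules, and SAP section 14 declares no departure from the protocol.

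On weight, Protocol 6.11 says that the subject's "weight in kilograms will be determined before the start of each cycle" and bases each subject's dose on the assigned level and weight in kilograms.

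**The concern.** There are two separate mismatches between the SAP formula and the way the drug is given.

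First, a programmer following SAP 8.8 must assign a q28d subject 21 days (or 14) after the last dose. The final interval is cut short, duration is understated, and dose intensity comes out above plan for someone dosed exactly as planned.

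Second, the numerator is mg calculated from the weight at each cycle, while the denominator uses the weight at baseline. A subject who receives the full assigned mg/kg every time then shows an RDI below 100% after weight loss and above 100% after weight gain.

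What is at stake is the accuracy of a descriptive exposure table that SAP 8.8 presents by cohort, in a study that may use more than one schedule.

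**Working it through.** The documents state no numerical value for exposure or RDI, so there is no figure to reproduce. The SAP formula was applied directly to a subject who receives every dose in full and on time, for whom RDI should be 1.000.

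**Inputs.** Days added: 14 or 21 (SAP 8.8). Cycle lengths: 14, 21 or 28 days (protocol synopsis, Table 4 notes, section 6.3). Dosing by weight taken before each cycle (Protocol 6.11).

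**Assumptions.** Planned dose intensity is the assigned mg/kg per planned cycle length. Duration of treatment equals duration of exposure. The end of treatment date does not cut the last interval, except in step 3. All weight changes are hypothetical.

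**Formula.** Let n be the number of doses, c the cycle length, a the days added, d the assigned mg/kg, W0 baseline weight and Wi the weight at dose i.

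- Duration = c(n − 1) + a
- Actual intensity = d × ΣWi / (W0 × duration)
- Planned intensity = d / c
- RDI = c × Σ(Wi/W0) / [c(n − 1) + a]

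**Step 1: schedules the SAP covers, stable weight.** With c = a = 14 or c = a = 21, RDI = cn/cn = 1.000 for every n. The formula is correct there.

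**Step 2: q28d, stable weight.** RDI = 28n / [28(n − 1) + a].

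| Doses | a = 21 | a = 14 |
|---|---|---|
| 1 | 28/21 = 1.333 | 28/14 = 2.000 |
| 2 | 56/49 = 1.143 | 56/42 = 1.333 |
| 4 | 112/105 = 1.067 | 112/98 = 1.143 |
| 6 | 168/161 = 1.043 | 168/154 = 1.091 |
| 8 | 224/217 = 1.032 | 224/210 = 1.067 |

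The a = 21 column is the milder reading. The shortfall is 28 − 21 = 7 days there, or 28 − 14 = 14 days if 14 is used.

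**Step 3: the end-of-treatment limit.** If that date falls t days after the last dose, the SAP counts min(21, t) days where the 28-day rule would count min(28, t). The gap is 7 days when t ≥ 28, t − 21 days when t lies between 21 and 28, and zero when t ≤ 21. The limit can make the two rules agree by shortening both. It never restores the missing days.

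**Step 4: weight, with c = a.** RDI reduces to the mean of Wi/W0.

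- 10% loss, linear from first to last dose: (1 + 0.9)/2 = 0.950
- 5% loss, linear: (1 + 0.95)/2 = 0.975
- 10% gain, linear: (1 + 1.1)/2 = 1.050
- 10% loss present from cycle 2 of 6: (1 + 5 × 0.9)/6 = 5.5/6 = 0.917

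**Step 5: both together.** For q28d with a = 21 and a linear 10% loss, 2 doses give 28 × 1.9/49 = 1.086 and 8 doses give 28 × 7.6/217 = 0.981. The two errors partly offset.

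**After correction.** With a = 28 for q28d, and each dose divided by the weight used for it, RDI is 28n/28n = 1.000 whatever the number of doses or the weight change.

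**The case against.** The strongest reply is that little depends on this, and much of that reply stands.

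- The 28-day schedule is optional. The study starts on 21 days, and neither document shows that a 28-day cohort was opened. If none was, the first mismatch has no effect.
- The q28d inflation shrinks with further dosing, to about 4% after 6 doses and 3% after 8.
- The RDI figures depend on how planned dose intensity is defined. If it were computed over the same shortened duration, the error could cancel in the ratio. Duration of exposure, which SAP 8.8 summarizes in its own right, would still be short.
- RDI above 100% is not peculiar to q28d. An end of treatment date before the end of the last interval can produce it on q14d or q21d as well.
- Protocol 6.11 does not expressly say that mg is recalculated each cycle, and it refers to a Pharmacy Binder not available here. Recalculation is the natural reading of weighing before every cycle for a weight-based dose. Dividing by baseline weight is a stated definition with a drawback, not a slip of arithmetic.

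A reader might also infer that RDI is wrong throughout the trial, or that cohorts and schedules will be misjudged for tolerability. The documents support neither. Step 1 shows the formula is right for stable-weight q14d and q21d subjects. RDI appears only in SAP 8.8. Tolerability is addressed through DLTs and delayed DLTs by cohort (SAP 10.1) and adverse events, including those leading to delay, interruption, reduction or discontinuation (SAP 10.2). Protocol 10.1 makes all analyses descriptive.

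What does not stand is the idea that the end-of-treatment limit repairs the 28-day gap. It can only shorten duration.

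**Conclusion.** The point holds for two groups: q28d subjects, if that schedule is used, and subjects whose weight changes. Applied as written, SAP 8.8 gives them inaccurate exposure figures, and no other section supplies a 28-day rule.

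The duration error is 7 days with the 21-day value, and less if the end of treatment date falls before day 28. The RDI consequence, 133% falling to about 103% between 1 and 8 doses, rests on the assumptions listed in the working, chiefly the definition of planned dose intensity. The weight effect, about 92% to 95% for a 10% loss, illustrates a hypothetical change and also assumes that mg follows current weight.

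This is a minor point. No endpoint, sample size or dose decision depends on RDI. It is worth correcting because the repair is specific and nearly free.

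**What to change.** Amend SAP 8.8 in four places:

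1. Duration of exposure: *plus 14, 21 or 28 days according to the dosing interval in force at the last dose*. The end-of-treatment limit stays.
2. Actual dose intensity: the sum over cycles of mg given divided by the weight used for that cycle's dose, all divided by duration of exposure.
3. Planned dose intensity: the assigned mg/kg per planned cycle length.
4. One term for duration in both formulas.

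The second change works whichever weight the pharmacy applied, provided that weight is on record. Weight is already determined before each cycle under Protocol 6.11. The cost is SAP wording and minor programming. Nothing changes in dosing, visits or data collection.

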### **6.3 Treatment Period**

Subjects who meet the selection criteria may start NKTR-214 treatment within 28 days following the Screening visit. The treatment period of the study is divided into multiple 21-day cycles with associated evaluations and procedures. Results of the assessments must be reviewed and documented before administering the first dose of the next cycle. No subject will be permitted escalation of dose level after assignment to a specific NKTR-214 dose level. Dose reductions after Cycle 1 due to AEs may occur following a discussion with the site Investigator and Medical Monitor. Every effort should be made to schedule visits within the protocol-specified windows.

For each dose level in Part 1, the first subject enrolled into a given dose cohort will be treated and monitored from Cycle 1, Day 1 through Cycle 1, Day 5 for safety and tolerability prior to dosing of additional subjects at that dose level.

Cycle 1, Day 1 will be the first day of treatment with NKTR-214 and Cycle 2, Day 1 will be the first day of the second dose of NKTR-214. Results from Day 1 laboratory evaluations must meet eligibility criteria prior to Cycle 1, Day 1 dosing.

During dose escalation, subjects who drop out prior to completion of Cycle 1 will be replaced unless the subject discontinued due to a DLT. During dose expansion, subjects will not be replaced.

Subjects will be treated until unacceptable toxicity, or disease progression per RECIST version 1.1. In the presence of disease progression, treatment may continue if there is clinical benefit as determined by the Investigator based on a reduction of symptoms related to cancer and absence of clinical deterioration or decline in ECOG performance status.

Note: Dosing may change to q14d or q28d following review and agreement by the Sponsor and Investigators. The change in cycle length will be determined by review of safety data and PK review of study drug.

After completing the pre-dosing procedures, administer NKTR-214 as an IV infusion over  $15 \pm 5$  minutes (Section 6.11).

Postdosing:

- The study site must be equipped for medical emergencies and have access to an intensive care unit.
- During dosing days, subject will stay in clinic for observation approximately 1 hour after dosing.
- Administer at least 2 liters of fluid (IV or self-administered orally [e.g., fluid containing electrolytes]) during Days 1 to 5 of every cycle.

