### **6.5 Post-treatment Period**

The EOT/Early Termination visit is to occur within 30 days (+ 10 days) after last dose of study drug.

Subjects who reach the EOT visit without radiographic disease progression must continue to undergo immunogenicity testing and radiological assessment at the interval of every 3 months ( $\pm 7$  days) until either disease progression per RECIST version 1.1 or the start of a new anti-cancer therapy. Subjects will also be followed every 3 months ( $\pm 7$  days) for survival until death, lost to follow-up, study termination by Sponsor, or 3 years have passed since the subject's first dose.

For any toxicity the Investigator attributed to study drug, the Investigator will assess the subject to determine whether the toxicity resolved or worsened. Information on whether the toxicity resolved or worsened must be entered into the eCRF.

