## 6.10 Dose Modifications

### 6.10.1 Non-immune-related Adverse Events

- Grade 1 or 2 toxicity: No requirement for dose delay or dose reduction. If the toxicity persists at Grade 2 following completion of Cycle 1, a dose reduction to the next lower NKTR-214 dose level (for dose escalation) or 50% of the assigned dose (dose escalation or dose expansion) may be implemented at the discretion of the Investigator with the approval of the Medical Monitor.
- Grade 3 toxicity: NKTR-214 may be withheld if toxicity cannot be managed by adequate medical intervention. NKTR-214 dosing may resume at the same dose or the next lower NKTR-214 dose level (for dose escalation) or 50% of the assigned dose (dose escalation or dose expansion) when toxicity resolves to Grade 1 or returns to baseline, except for instances consistent with clinically significant capillary leak syndrome or where the potential recurrence of the event poses an undue risk for the subject.
- Grade 4 toxicity (excluding Grade 4 transient lymphopenia < 14 days in duration): Dosing should be permanently discontinued.

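### SAP 8.8 counts the last dose in full but can cut its interval at an undefined end of treatment date, so relative dose intensity can be overstated for subjects who stop early

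*SAP*

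**What the plan says.** SAP 8.8 summarizes RDI for each cohort. Cumulative dose is the sum of "actual dose within each study cycle", so the final dose enters whole. Duration of exposure runs from the first dose to the last dose "plus 14 or 21 days depending on NKTR dosing frequency or end of treatment date, whichever is earlier". On RDI the section says: "The relative dose intensity is calculated as the actual dose intensity divided by the planned dose intensity". Actual dose intensity is the "total cumulative dose divided by weight at baseline and duration of treatment".

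Three terms in this derivation have no definition: *end of treatment date*, *duration of treatment* and *planned dose intensity*. The only duration that the section defines is the duration of exposure.

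Protocol 6.5 describes a visit that may or may not supply the date meant: "The EOT/Early Termination visit is to occur within 30 days (+ 10 days) after last dose of study drug". On cycle length, Protocol 6.3 says "The treatment period of the study is divided into multiple 21-day cycles", and the notes to Protocol Table 4 add: "The schedule of dosing can be modified to every 14 or 28 days". SAP 8.8 gives no interval for the 28-day schedule.

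**The concern.** A dose intensity compares the drug given with the time it was meant to cover, and each dose is planned to cover one interval. If the end of treatment date falls inside the last interval, the numerator keeps the whole last dose while the denominator loses the rest of its interval. The two then cover different periods, and the ratio can only move upward.

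RDI is read as a tolerability summary by dose cohort. A value pushed upward in subjects who stop soon after a dose would make delivered dose look better than it was, and could offset a late or reduced dose. Early stops are plausible here. For most Grade 4 non-immune toxicity, Protocol 6.10.1 says "Dosing should be permanently discontinued", and Protocol 6.9 expects drug-related toxicity mainly during treatment or in the 10 days after it.

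**Working it through.** The documents state no RDI figure, so there is none to reproduce.

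**Inputs from the documents**
- Last interval credited: 21 or 14 days, or less if the end of treatment date is earlier (SAP 8.8).
- Numerator: all actual doses, the last in full (SAP 8.8).
- Reduced dose: 50% of the assigned dose (Protocol 6.10.1).
- Longest delay before a dose counts as missed: 7 days (Protocol 6.12).

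**Assumptions, not in the documents**
- Duration of treatment means duration of exposure.
- Planned intensity is one assigned mg/kg dose per interval.
- Weight is constant.
- The gap *k* from last dose to end of treatment date is 7, 14, or 21 or more days.

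**Formula.** With *S* the sum of doses as fractions of the assigned dose, *τ* the interval and *L* the days from first to last dose:

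RDI = *S* × *τ* / (*L* + min(*τ*, *k*))

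Check: with *k* ≥ *τ* and two full doses on the 21-day schedule, 2 × 21 / (21 + 21) = 100%. Any number of on-schedule full doses also gives 100%.

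**On-schedule full dosing, 21-day schedule**

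| Doses | *k* = 7 | *k* = 14 | *k* ≥ 21 |
|---|---|---|---|
| 1 | 21/7 = 300% | 21/14 = 150% | 100% |
| 2 | 42/28 = 150% | 42/35 = 120% | 100% |
| 4 | 84/70 = 120% | 84/77 = 109.1% | 100% |

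On the 14-day schedule with *k* = 7, one, two and four doses give 14/7 = 200%, 28/21 = 133.3% and 56/49 = 114.3%. With *k* ≥ 14 the value is 100%.

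**Reduced, late or missed doses, 21-day schedule, *k* = 7**

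| Pattern | With the cut | Without the cut |
|---|---|---|
| 2 doses, second halved | 31.5/28 = 112.5% | 31.5/42 = 75.0% |
| 2 doses, second 7 days late | 42/35 = 120.0% | 42/49 = 85.7% |
| 3 doses, 50% from dose 2 | 42/49 = 85.7% | 42/63 = 66.7% |
| 4 doses, 50% from dose 2 | 52.5/70 = 75.0% | 52.5/84 = 62.5% |
| 2 doses, one missed between them | 42/49 = 85.7% | 42/63 = 66.7% |
| 4 doses, one missed before the last | 84/91 = 92.3% | 84/105 = 80.0% |

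The first two patterns rise above 100%. The other four stay below 100% but are still overstated.

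**Effect on a cohort summary.** Escalation cohorts start at 3 subjects (Protocol 4.1.2.1), and SAP 5 reports mean, median, minimum and maximum. Take one single-dose subject with *k* = 7 and the rest at 100%. The mean is (100 + 100 + 300)/3 = 166.7% with three subjects and (5 × 100 + 300)/6 = 133.3% with six. The maximum is 300% and the median stays at 100%.

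**A separate gap.** For the 28-day schedule, if the 21-day interval is used for want of another, on-schedule full dosing gives 28/21 = 133.3% after one dose and 56/49 = 114.3% after two, even when end of treatment is 30 days after the last dose.

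**The case against.** The strongest reply is that the cut may never take effect. If the end of treatment date is the Protocol 6.5 visit and that visit takes place near day 30, RDI is unchanged in every 14-day and 21-day pattern above. This stands as a condition. It does not settle the matter, because the protocol allows the visit any time within the 30 days and the SAP does not say that the visit is the date meant. The date treatment was stopped, an early visit or a death could all come sooner.

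Second, SAP 8.8 applies the cut to duration of exposure but divides by duration of treatment, and it leaves planned intensity open. If planned intensity were the planned dose over the same shortened time, the cut would cancel. This also stands. The inflation rests on the natural reading of the section, not on its stated text. On any other reading the RDI denominator is undefined and still needs a sentence.

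Third, RDI feeds no DLT, MTD or ORR decision. SAP 8.8 also reports infusions and cumulative dose and lists exposure by subject. SAP 10.2 tabulates adverse events leading to delay, interruption, reduction or discontinuation. All of this is correct and limits the consequence to the RDI summary.

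A reader might infer that the rule hides dose reductions and delays in general. The working does not support that. Reductions to 50% from the second dose over three or more doses, and missed doses, remain below 100%, and the effect shrinks as doses accumulate. A reader might also infer that the worst-tolerated cohorts are inflated most. The documents do not say when subjects stop relative to a dose or how the end date is recorded, so that ranking cannot be shown.

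**Conclusion.** The concern holds conditionally. Under the two assumed definitions, RDI is overstated for every subject whose end of treatment date falls before last dose plus one interval, and is unaffected otherwise. The size depends on the gap, which the documents do not give, and on the number of doses. For on-schedule full dosing on the 21-day schedule it ranges from no effect at 21 days or more to 300% for a single dose at 7 days. A single reduced or late final dose after few doses can be lifted above 100%.

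The consequence is confined to a descriptive table, where the mean and maximum of a small cohort can overstate delivered dose. The documents do not support saying that RDI will exceed 100% for early stoppers as a rule, because the date that controls the cut is undefined. This is a correction that the SAP should make, not a threat to the trial's main conclusions.

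**What to change.** In SAP 8.8:

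- Compute actual dose intensity over date of last dose minus date of first dose plus the planned dosing interval of the subject's schedule, with no cut at the end of treatment date.
- Define planned dose intensity as the assigned dose per planned interval.
- Define *end of treatment date*, and say whether it is the visit, the date treatment was stopped or something else.
- Keep the whichever-is-earlier rule only for the separate summary of duration of exposure, and add the 28-day interval there.

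The change either leaves a subject's RDI as it is or removes an upward bias. Because the interval follows the subject's schedule, it also brings on-schedule 28-day dosing to 100%. The cost is one rewritten sentence, short definitions and one derivation line, with no change to conduct or data collection. The downside is that some reported RDI values become lower.
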